13.3. Calculation of Sample Size

13.3.1. Total Sample Size

The number of evaluable subjects required for this trial is 210 subjects (105 per treatment arm). In order to account for a potential 10% drop-out rate, at least 234 subjects (117 per treatment arm) will be randomized into the trial in a 1:1 allocation ratio SURGICEL Powder to SURGICEL Original.

Two hundred and ten (210) evaluable subjects (105 per study arm) will achieve 80% power to detect a non-inferiority margin difference in group proportions of 0.1 using a Farrington-Manning score test with a one-sided significance level of 0.025. The proportion of successes in the Control group is assumed to be 0.8. The proportion of successes in Test group is assumed to be 0.7 under the null hypothesis of inferiority. The power was computed for the case when the actual proportion of successes in the Test group is 0.85.

13.3.2. Minimum and Maximum Number of Subjects in Each Clinical Trial Institution and Reasons for Determination

A total of 234 subjects will be enrolled in approximately 12 study sites. The number of subjects enrolled in any site should not exceed 46 subjects (20% of the total sample size).

13.4. Significance Level and Power of Clinical Trial

The power of the statistical test at which the sample size for the primary endpoint was calculated is 80%, and the one-sided significance level of the test was set to 0.025.

For the primary effectiveness endpoint, a one-sided 97.5% confidence interval for P_T - P_C will be constructed using the Farrington-Manning (FM) score method. In addition, two-sided 95% confidence intervals for the proportion of successes in each treatment group separately will be constructed using the Clopper-Pearson method.

For the binary (success/failure) secondary effectiveness endpoints (3 and 10 minutes hemostasis endpoints), within-treatment group two-sided 95% confidence intervals will be reported for the proportion of successes using the Clopper-Pearson method. A two-sided 95% confidence interval for the difference in proportion of successes between treatment groups (Test minus Control) will also be calculated for each binary secondary effectiveness endpoint using the FM score method.

Confidential Page 66 of 86

13.5. Expected Dropout Rate

The expected dropout rate in this study is 10%.

13.6. Criterion of Acceptability/Unacceptability of Clinical Trial Result

For the primary effectiveness endpoint, a one-sided 97.5% confidence interval for P_T - P_C will be constructed using the Farrington-Manning (FM) score method. If the lower limit of the one-sided 97.5% confidence interval is greater than -0.1, then it will be concluded that the SURGICEL Powder is non-inferior to SURGICEL Original. If the non-inferiority of SURGICEL Powder is established, the superiority of SUGICEL Powder to SURGICEL Original will then be evaluated; if the lower limit of one-sided 97.5% confidence interval is greater than 0, then it will be concluded that the SURGICEL Powder is superior to SURGICEL Original.

13.7. Criteria and Reason for Terminating the Trial Based on the Statistical Results

13.8. Early termination of this trial is not applicable since no formal interim analyses are planned. Statistical Method of All Data, together with the Handling Method of Missing, Unused and Error Data (including Termination and Withdrawal Halfway) and Unreasonable Data

It is not anticipated that there will be data missing for the primary or secondary effectiveness endpoints, but, if there is, the analyses based on the ITT set will consider missing data as failures for these endpoints. Missing data for safety endpoints will not be imputed.

13.9. Reporting Procedure of Deviation from Original Statistical Plan

Any changes from the original planned statistical analyses will be specified in the protocol revisions, if applicable, and/or in a final or amended statistical analysis plan. The impact of these changes on any conclusions of the study will be detailed in the final Clinical Study Report.

13.10. Selection Criteria and Reason of Subjects Included in the Analysis

All subjects that meet the inclusion/exclusion criteria are considered to meet the requirements for recruitment. Definitions of analysis sets are included in Section 10.1.

14. DATA MANAGEMENT

The individual subject data collected during the period of this trial will be recorded in the corresponding study database. The captured data will be reviewed by the data

Confidential Page 67 of 86

03 SEP 2019, VERSION: 1.1

management team and other applicable Sponsor study team members. Any unexpected or missing data points will generate a query for the site to assess and resolve. Sponsor provided monitors will be available for questions and follow-up with the sites, as needed.

When all subjects complete all follow-up evaluations and the corresponding data is entered, this study will be closed and the data analysis will be performed following database lock.

15. FEASIBILITY ANALYSIS

15.1. Likelihood Analysis of Success

Adjunctive topical hemostatic agents have been utilized for over 100 years. The equivalent comparator to SURGICEL Powder, SURGICEL Original, has been available for more than 50 years, introduced in 1960 with a long history of safe and efficacious use.

SURGICEL Original and its family of products has predominately been used to assist in achieving and accelerating hemostasis, during which several types of bleeding have been observed intra-operatively. These types of products are optimal when bleeding is confined, because the product can be placed on the source of bleeding with manual compression to facilitate hemostasis. When bleeding is not confined, continuous oozing from large friable and raw surfaces can cause delays and surgeon frustration during surgery. These situations require ready to use hemostatic products with minimal or no preparation time and in addition must be able to achieve quick coverage on the bleeding surface and the ability to achieve hemostasis.

SURGICEL Powder, an optimized powdered form of ORC, is a topical absorbable hemostat being evaluated in this study to further measure its safety and hemostatic effectiveness in controlling mild to moderate parenchymal or soft tissue intra-operative bleeding. Although there is sufficient information supporting the safety and performance of SURGICEL Powder supported by data from acute and survival preclinical studies (see Section 8), this registration study will be implemented to further enhance our understanding of safety and performance of SURGICEL Powder in a real world clinical setting.

15.2. Likelihood Analysis of Failure

In recent years, adjunctive topical hemostatic agents are gaining momentum in China. Because of this growing popularity as well as the state of the art optimized powder form of ORC, failure to meet total enrolment (234 patients) as stipulated by the protocol, is

Confidential Page 68 of 86

ETHICON, LLC. BIOS_2017_02

03 SEP 2019, VERSION: 1.1

unlikely. Also, because of the long history of safe and efficacious use of the SURGICEL family of products, it is unlikely that the study will be discontinued because of safety concerns.

16. PRODUCT MANAGEMENT

All products must be stored in conditions according to product labeling and IFU/IB. It is the responsibility of the Principal Investigator to ensure that products are stored correctly at the site.

The Principal Investigator or responsible person designated by the Principal Investigator must account for all study products throughout and, at the end of, the clinical study. During the course of the study, the study products must be stored in a locked or secure access location. An inventory record must be maintained of all products received, used or returned during the clinical trial. Details of the product code and lot numbers must be documented in the CRF as well as the subject's hospital notes. The Principal Investigator must allow the Monitor access to the secure facility where the study products are stored during the clinical trial in order to check inventory. At the end of the clinical trial all unused study products must be returned to Johnson & Johnson Medical (Shanghai) Ltd. with the appropriate study product return form.

17. QUALITY CONTROL OF CLINICAL TRIAL

During the clinical study, the Sponsor and Investigator should execute their respective responsibilities according to the Good Clinical Practice for Medical Product Trials and applicable related Chinese and international regulations. They should also strictly follow the clinical trial protocol to ensure the quality of clinical trial.

The Sponsor will ensure proper training on the clinical trial protocol and the use and maintenance of investigational medical product for all investigators participating in the trial, so as to ensure the consistency in the implementation of clinical trial protocol, the use of investigational medical product.

During the implementation of study, the Sponsor is responsible for monitoring each phase of the clinical trial. The clinical monitor employed by the Sponsor or appointed representative should comply with the related standard operating procedure (SOP) and clinical trial protocol that are established by the Sponsor to monitor the clinical trial, so as to ensure the complete, accurate, true and reliable data.

To ensure the quality of study, the Sponsor may authorize the eligible QA auditor to audit the clinical trial, as needed. The Investigator should allow the auditors to review the

Confidential Page 69 of 86

original data and documents related to this study after receiving the notification.

When the food and drug regulatory authority, competent department of health and family planning or other regulatory agencies send the inspection personnel to carry out the inspection, the clinical trial institution and Investigator should cooperate and immediately notify the Sponsor.

18. CLINICAL TRIAL-INVOLVED ETHICAL ISSUES AND INFORMED CONSENT

18.1. Ethical Concerns

Participating Investigators will ensure that this protocol, the ICF, and if applicable, any protocol amendments or other written information provided to the subjects that assist in the decision to participate are reviewed by an Institutional Review Board (IRB) or Ethics Committee (EC) that complies with governmental requirements. The approving IRB/EC will be responsible for the initial and continuing review and approval of this clinical investigation. Participating investigators will be required to promptly report to the IRB/EC as required by the IRB/EC's policies. Additionally, investigators will be required to refrain from making any changes in the clinical investigation plan without Sponsor and IRB/EC approval of an amended protocol, except where necessary to eliminate apparent immediate hazards to study subjects or others.

Before the subjects participate in the clinical trial, the Investigator must fully explain this study and answer all questions raised by subjects. Each subject (or legally authorized representative) must voluntarily sign and date the informed consent form (and other documents as per local regulations) that is approved by the Ethics Committee prior to implementing any study-related tests or procedures which are not SOC. The process of obtaining the informed consent needs to be clearly documented in the original record of the subject. The subject may request to withdraw the informed consent at any time during the study. This withdrawal will not affect the subsequent therapy of available / provided to the subject.

The production of investigational product should meet the relevant requirements of applicable quality management system for medical products. The processing and storage of investigational product should meet the requirements of specifications and related standard operating procedure. The investigational product should be used according to the approved protocol and related operation instructions and IFU/ IB.

The collection, use and disclosure of all personal data (including the subject health and medical information) should comply with the applicable laws and regulations with regard

Confidential Page 70 of 86

to the personal data protection and security. When collecting and processing such personal data, appropriate measures are to be taken to maintain the confidentiality of subject health and medical information and to prevent access by unauthorized persons.

18.2. Approval of Trial Protocol

The trial protocol should be internally approved and filed according to the company's SOP prior to submitting to the external agency (including but not limited to the government regulatory agencies, Ethics Committee).

The clinical trial protocol should not be implemented until the written approval is obtained from the Ethics Committee according to the relevant requirements of laws and regulations.

18.3. Process of Informed Consent and Text of Informed Consent Form

18.3.1. Process of Informed Consent

The informed consent of all potential subjects must be obtained prior to performing any study tests/procedures that are not SOC. Once the Investigator determines that the subjects are suitable for participating in this study, the Investigator must explain the background of the study presented and the benefits and risks of surgery and study to the subjects and answer the questions raised by subjects. Only the subject who signs the informed consent form that is approved by the EC prior to participating in the study is eligible to participate in this study.

Each subject (or legally authorized representative) must sign and date the informed consent form that is approved by the EC (and other documents as per local regulations) prior to implementing any study-related items or operations not belonging to the standard treatment and after the nature of this study is fully clarified.

The process of obtaining the written informed consent needs to prove that the subjects volunteer to participate in this study. All aspects of this study must be clarified to the subjects prior to signing the informed consent form. The process of obtaining the informed consent must be clearly documented by the Investigator and/or designated person in the original clinical trial documents of subjects. The Investigator has responsibilities to ensure the process of obtaining the informed consent is implemented according to the Good Clinical Practice for Medical Product Trials and related regulations, such as ISO 14155, the Declaration of Helsinki.

18.3.2. Text of Informed Consent Form

The ICF is available as a separate attachment.

Confidential Page 71 of 86

19. REGULATIONS OF ADVERSE EVENT AND PRODUCT COMPLAINT REPORTING

19.1. Adverse event

Adverse Events associated with the device, or the procedure, and incidents such as those specified in local laws and regulations will be captured and reported during this study. Monitoring of study sites by Sponsor personnel will ensure that adverse events and product complaints are documented.

19.2. Definitions

19.2.1. Pre-existing Condition

A pre-existing condition is one that is present at the start of the study, and is to be reported as part of the subject's medical history. It must be reported as a new Adverse Event if the intensity, frequency, or the character of the condition worsens during the study treatment.

To avoid confusing pre-existing conditions with AEs during data analysis, the study sites must make all attempts to provide start dates for all baseline medical conditions. Any pre-existing condition that has worsened in intensity, frequency, or the character of the condition should be recorded on the AE eCRF as an exacerbation of the pre-existing condition and the start date will be recorded as the time when the exacerbation occurred.

19.2.2. Adverse Event

For this study, an AE is an untoward medical occurrence (sign, symptom or disease) in a subject or clinical trial subject and which does not necessarily have a causal relationship with the study medical device. An untoward medical occurrence includes any new, undesirable medical experience or worsening of a pre-existing condition.

Enrollment through the 30-Day Follow-Up: All AEs, whether attributable to the device/procedure or not, are to be recorded in the eCRF and reported to the Sponsor.

19.2.3. Adverse Device Effect

An Adverse Device Effect (ADE) is an adverse event related to the use of a study medical device. This includes any adverse event resulting from insufficient or inadequate Instructions for Use, deployment, implantation, or operation, or any malfunction of the study medical device. An ADE may also include any event resulting from use error or from intentional misuse of the study medical device.

Confidential Page 72 of 86

19.2.4. Unexpected Adverse Device Effect

An unexpected ADE is an adverse device effect, the nature or severity of which is not consistent with the applicable product information (e.g. Investigator's Brochure or product labelling).

19.3. Serious Adverse Event

It is the investigator's responsibility to determine the "seriousness" of an AE using the protocol defined terms below. An SAE is any AE that results in any of the following:

- Death or a life-threatening event.
- Inpatient hospitalization or prolongation of hospitalization.
- Persistent or significant disability/incapacity.
- Congenital anomaly/ birth defect//led to fetal distress, fetal death

Notes:

- 1. "Death" should not be reported as an AE. The cause of death should be reported as an AE. The only exception is "Sudden Death," when the cause is unknown.
- 2. Planned hospitalization for a pre-existing condition is not considered an SAE.
- 3. A procedure required by the protocol is not considered an SAE, unless the subject experiences a serious deterioration in health or hospitalization is prolonged.

Enrollment through 30-Day Follow-Up: All SAEs, whether attributable to the device/procedure, are to be recorded in the eCRF and reported to the Sponsor.

6-Month Follow-Up: SAEs requiring surgical intervention and assessed as possibly related or related to the study treatment are to be recorded in the eCRF and reported to the Sponsor.

Follow-up on all SAEs possibly related or related to the study treatment, which were ongoing at the 30-day post-surgery follow-up will be assessed.

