10.1.6. Criteria of Sponsor's Discontinuation of the Trial

Both the Investigator and Ethicon reserve the right to terminate the study at any time. Should this be necessary, the procedures will be arranged on an individual study basis after review and consultation with both parties. In terminating the study, Sponsor and the Investigator will ensure that adequate consideration is given to the protection of the subjects' interests and safety.

The Sponsor has the right to terminate the study early for a single site, multiple sites or all sites temporarily or permanently. Reasons may include, but are not limited to: safety issue or ethical issue, inaccurate or incomplete data record, non-compliance or dissatisfactory quality or quantity of the recruited subjects. Health authorities also have the right to terminate a study.

Confidential Page 45 of 86

The Sponsor's Medical Director (Study Medical Monitor/Safety Lead) will assess all SAES for causality and expectedness and will utilize Ethicon's Product Safety Committee (PSC) to review and adjudicate the following safety signals:

- Thromboembolic events
- Postoperative re-bleeding
- Reoperations for complications assessed as possibly related or related to the study treatment.

The PSC will also review cumulative safety data from the study. The PSC will advise on the continuing safety of study subjects and those yet to be recruited to the study. Based on cumulative data from the study, the PSC may recommend whether to continue, suspend, modify, or stop the study. At the conclusion of the study, the PSC will also give a final assessment of the safety of the product from this study. The composition, responsibilities, frequency of PSC meetings, handling of emergency situations, and documentation of PSC meetings will be specified in the Safety Management Plan (SMP).

Stopping Rules:

The rules outlined below will be used to determine if the clinical trial should be put on hold, contingent on PSC recommendations:

- If three confirmed thromboembolic SAEs (pulmonary embolism [PE] / deep vein thrombosis [DVT]) are reported and assessed as being related to SURGICEL Powder
- If one or more subjects develop post-operative bleeding and the TBS is confirmed as the cause of the re-bleeding. The relatedness of the SAE to SURGICEL Powder is to be determined by the following:
 - o Findings at re-operation
 - o Findings of TBS re-bleeding at autopsy (if applicable).

Flow of Sponsor's Discontinuation of the Trial:

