19.3.1. Serious Adverse Device Effect (SADE)

A serious adverse device effect is an adverse device effect that has resulted in any of the consequences characteristic of a serious adverse event or that might have led to any of these consequences if suitable action had not been taken or intervention had not been made or if circumstances had been less opportune.

Confidential Page 73 of 86

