19.6.2. Reporting Non-Serious Adverse Events to the Sponsor

Enrollment through 30-Day Follow-Up:

All non-serious AEs, whether attributable to the device/procedure or not, will be reported from time of enrollment, during the surgical procedure, and until completion of the 30-day follow-up. For all non-serious AEs, the study site is expected to complete the Adverse Event eCRF within 2 weeks of becoming aware of the event. Supporting documentation may be requested, as needed.

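### Safety endpoint 3 counts only SAEs that need surgery, but Protocol 19.3 does not class averted harm as serious, so some treatment-related re-operations fall outside it

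*Protocol*

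**What the plan says.** Protocol 19.3 opens its definition with "An SAE is any AE that results in any of the following" and then lists four groups of outcome: "Death or a life-threatening event"; "Inpatient hospitalization or prolongation of hospitalization"; "Persistent or significant disability/incapacity"; and "Congenital anomaly/ birth defect//led to fetal distress, fetal death". No item covers medical or surgical intervention that prevents one of these. The notes under the list deal with how deaths are recorded, planned admissions and protocol-required procedures, and do not widen it.

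Protocol 19.3.1 (SADE) is wider. It takes in a device effect that led to one of the serious outcomes, and also one "that might have led to any of these consequences if suitable action had not been taken or intervention had not been made".

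Safety endpoint 3 (Protocol synopsis, 10.1.4, 10.1.13 and 13.2; SAP 14.1) is the incidence of SAEs that need surgery and are judged at least possibly related to study treatment, from enrollment to the 6-month contact. The SAP gives no SAE definition of its own.

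Protocol 10.1.6 and 10.1.13 name, among the signals for the Product Safety Committee (PSC), "Reoperations for complications assessed as possibly related or related to the study treatment".

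On timing, Protocol 19.6.1 requires SAEs to reach the sponsor within 24 hours. For non-serious events up to day 30, Protocol 19.6.2 says that "the study site is expected to complete the Adverse Event eCRF within 2 weeks of becoming aware of the event". Protocol 19.6.3 sets 24 hours for unexpected device effects (UADEs). Under Protocol 10.1.13, the 6-month contact takes in only related SAEs that need surgery.

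**The concern.** Endpoint 3 exists to capture surgery made necessary by the study product. An event must first qualify as an SAE, and the SAE list looks only at what the event led to. It does not look at what surgery prevented. A prompt re-operation that works, and that does not lengthen the stay, can therefore leave the event non-serious and outside the endpoint.

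The protocol already has the missing idea one subsection later, but attaches it to a term that the endpoint does not use. Sections 19.3 and 19.3.1 thus apply different tests of seriousness to the same event.

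Two things are at stake: the completeness of a safety endpoint in which every event weighs heavily, and the speed at which the sponsor hears of such an event.

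**Working it through.** The plan states no figure on this point, so the check is a comparison of definitions. Each case below is an event that needs surgery and is at least possibly related to study treatment.

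| Case | SAE under 19.3? | In endpoint 3? | Captured elsewhere? |
|---|---|---|---|
| Life-threatening | Yes | Yes | – |
| After discharge, inpatient admission needed | Yes | Yes | – |
| During index stay, stay prolonged | Yes | Yes | – |
| During index stay, stay not prolonged, no threat to life or disability; for re-bleeding | No | No | Endpoint 2 to day 30; AE record |
| Same, for another complication | No | No | AE record to day 30 |
| Outpatient procedure to day 30, no threat to life or disability | No | No | AE record; endpoint 2 if re-bleeding |
| Outpatient procedure after day 30, no threat to life or disability | No | No | Not asked for at the 6-month contact |

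The steps behind the table:

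1. **Seriousness.** The list in 19.3 is closed. An event with none of the four outcomes is non-serious, whatever the surgery prevented.
2. **Endpoint 3.** Protocol and SAP both count SAEs. Neither says that a SADE counts as an SAE for this purpose.
3. **Endpoint 2.** Re-bleeding that needs medical or surgical intervention is counted to day 30 with no seriousness test. The SAP changes the relatedness term from the target bleeding site to the study treatment, but adds no such test.
4. **AE record.** All AEs are recorded to day 30 (Protocol 19.2.2, 19.6), and re-operation is named in the data for discharge and day 30 (Protocol 11.5, 11.6). SAP 14.1.1 and 14.2 tabulate AEs by relationship, severity and seriousness. No planned table shows AEs that needed surgery.
5. **After day 30.** Only related SAEs needing surgery are collected as new events (Protocol 10.1.13). A non-serious event is not required by that rule. Section 19.6.3 states no end date, so it could still reach an unexpected device effect, but that does not put the event into endpoint 3.
6. **Timing.** SAEs and UADEs are due in 24 hours. Section 19.2.4 defines an unexpected device effect with no seriousness test. The 2-week period therefore applies to an event that is both non-serious and not a UADE.

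**Size per event.** Planned allocation is 117 per arm, so one missed subject changes the arm's incidence by 1/117 = 0.0085, or 0.85 percentage points. The Safety set counts treated subjects; if fewer than 117 are treated, the step is slightly larger.

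**The case against.** **The two definitions can be read together.** Every event in endpoint 3 is at least possibly related to treatment, section 19.2.3 calls a device-related AE an adverse device effect, and 19.3.1 gives the test for a serious one. An investigator could apply the wider test to exactly the events that endpoint 3 is meant to cover. This reading is possible, but nothing in either document directs it. Section 19.3 tells the investigator to judge seriousness by the terms listed there. Two sites could classify the same re-operation differently, which is a reason to reconcile the sections.

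**Little is lost.** To day 30 the event is in the AE data, re-bleeding has its own endpoint, and the gravest cases already qualify as SAEs. This stands, and it limits the point to a narrow class of events. It does not close the gap in endpoint 3 or after day 30.

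**The stakes are low.** Safety endpoints are summarized descriptively with no inference (Protocol 13.2). Effectiveness and sample size are untouched. This also stands.

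**The PSC would see these events anyway.** Related re-operations are a named signal, but the sentence that introduces the signals begins with the assessment of SAEs. Whether a non-serious re-operation reaches the committee is unclear. A reader might infer that SAE, SADE and PSC signal are three settled definitions with three different counts. The text supports that for SAE against SADE only.

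**Conclusion.** The inconsistency is real and worth correcting. Followed as written, 19.3 leaves out of endpoint 3 a related re-operation or outpatient procedure that is not life-threatening, neither prolongs nor requires an inpatient stay, and leaves no disability. This assumes that sites apply 19.3 literally and do not carry over the test in 19.3.1.

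The undercount cannot be sized. Each missed event is worth 0.85 points in its arm, but the documents give no rate of re-operation and no share that would be non-serious.

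Stronger readings are tempting, and the documents do not support them:

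- **That such events vanish from the trial.** To day 30 they are recorded. The new-event collection omits them only after day 30.
- **That 5 to 12 subjects would be missed.** An assumed re-operation rate of 2% to 5% gives 0.02 × 234 = 4.7 to 0.05 × 234 = 11.7. That would count all re-operations for complications, related or not and serious or not. The gap is a subset of unknown size.
- **That the 6.6% re-bleeding figure in Protocol 7 measures the gap.** It describes re-bleeding after use of the control product, not re-operation, and re-bleeding that needs intervention is already in endpoint 2.
- **That every such event moves to 2-week reporting.** UADEs keep the 24-hour rule.

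**What to change.** Either of two changes would do; they differ in reach.

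1. **Amend Protocol 19.3.** Add a criterion for events that required medical or surgical intervention to prevent one of the listed outcomes, in line with 19.3.1. This brings averted-harm events into endpoint 3, the 6-month collection and 24-hour reporting.
2. **Redefine endpoint 3 and the 6-month collection.** Count AEs that require surgery and are judged possibly related, probably related or related to study treatment, regardless of seriousness. The relatedness limit must stay, or surgery unconnected with the product would enter. This repairs the count, but leaves the reporting times as they are.

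Neither makes endpoint 3, SADE and PSC signal identical: SADE also covers non-surgical action and less fortunate circumstances. A sentence in 10.1.6 on whether the PSC receives non-serious re-operations would remove the remaining doubt.

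If the protocol can no longer change, add an SAP table of related AEs requiring surgery, by arm and regardless of seriousness, to day 30. The re-operation items and the action-taken field (Protocol 11.5, 11.6, 19.6) should supply the data. Events after day 30 that were never collected cannot be recovered.

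The cost of option 1 or 2 is a protocol amendment, with ethics approval if it is classed as major (Protocol 20), and updated eCRF guidance. Option 1 also brings a few more expedited reports. Since SAP 14.7 describes the deviation assessment in the past tense, events already recorded may need to be reclassified. The SAP table alone costs one output.
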